**Figure 1 Study Flow**

5.3 Rationale for Study Design and Treatment Regimens

5.3.1 Randomization

Group 1 (3.75 µg of MT-2766) and Group 2 (placebo) will be randomized. Age (< 65 and ≥ 65) will be used as stratification factors. On the other hand, Group 3 (1.875 µg of MT-2766) will be not randomized.

With regards to Group 1 and 2, randomization will be used to minimize bias in the assignment of subjects to two treatment groups, to increase the likelihood that known and unknown subject attributes (e.g. demographic and baseline characteristics) are evenly balanced across treatment groups and to enhance the validity of statistical comparisons across treatment groups within each Study Population. On the other hands, Group 3 will be not randomized because of its exploratory purpose.

5.3.2 Blinding

The study will be observer-blind to reduce potential bias during data collection and evaluation of the study endpoints. Group 1 (3.75 µg of MT-2766) and Group 2 (placebo) will be observer-blinded, on the other hand, Group 3 (1.875 µg of MT-2766) will be open-labeled.

Details of who will remain blinded during the study are presented in Section 5.4.2

5.3.3 Dose Selection and Treatment Regimens

In the study, a double dose levels of the MT-2766 (i.e. 3.75 µg or 1.875 µg CoVLP adjuvanted with AS03) will be tested in a two-dose regimen on Day 0 and Day 21.

The data from Phase 1 study (CP-PRO-CoVLP-019) in Canada clearly demonstrate the superiority of AS03 in the induction of anti-SARS-CoV-2 antibodies at all dose levels of CoVLP (3.75 µg, 7.5 µg and 15 µg,) compared to CoVLP alone. These data also suggest that

two doses of AS03-adjuvanted CoVLP are needed to achieve consistently high antibody responses in healthy adults since robust boosting in the Day 42 antibody response after two doses of AS03-adjuvanted CoVLP was observed at all dose levels, Medicago has decided to carry the lowest dose, 3.75 µg, forward into the Phase 2/3 study (CP-PRO-CoVLP-021). Medicago determined the dose for the current study to be 3.75 µg based on the dose selected for the Phase 2/3 study. In addition, Medicago would like to assess a dose of 1.875 µg, a half of 3.75 µg, because there were no apparent differences in the increase in neutralizing antibody titers at any dose level (3.75 µg, 7.5 µg and 15 µg) in the Phase 1 study. The dose of 1.875 µg provides half of the 1: 1 mixture of 3.75 µg of CoVLP and AS03 and therefore avoids the complexity of preparation of IMP. Half-dose AS03 has been tested in several influenza vaccine studies with satisfactory immune-boosting effects and slightly lower reactogenicity.

5.3.4 Route of Administration

The route of administration used for MT-2766 is the IM route, specifically in the deltoid muscle of the arm, since it reliable route of administration with good absorption compared to the subcutaneous route. The IM route was used in the Phase 1 and Phase 2/3 studies by Medicago.

5.4 Treatment Allocation and Blinding

5.4.1 Randomization

In the study, subjects in Group 1 and 2 will be randomized 4:1 to receive the 3.75 µg of MT-2766 and placebo. Eligible subjects will be randomized at the Day 0 visit using the interactive web response system (IWRS). Age (< 65 and ≥ 65) will be used as stratification factors.

No subjects will be randomized into the study more than once.

Subjects will be enrolled into treatment groups in the study based on a computer-generated randomization schedule prepared under the supervision of MTPC before the study. The details of treatment allocation will be specified in a separate procedure.

The treatment will be recorded along with a unique subject number for each subject.

5.4.2 Blinding

The study, Group 1 and Group 2, will be observer-blinded. Group 3 will be open label.

Until key code breaking of the study, the following individuals will not have access to treatment allocation (i.e. remain “blind”): the subjects, the Investigators and all personnel involved in the clinical conduct of the study (except the staff involved in the preparation and administration of the study vaccine), Sponsor, ICCC, and all personnel involved in sample analysis at the central and testing (Nab, ELISA, ELISpot, ICS [flow cytometry], serological, and virologic method SARS-CoV-2 diagnostics, etc.) laboratories.

Since the CoVLP formulation will have a different physical appearance and viscosity from the placebo, the site staff involved in the preparation and administration of the treatments will not be involved in any activity that could introduce a bias, such as the evaluations of reactogenicity

or AEs experienced by the subjects following vaccination.

5.5 Key Open

Key open will be performed after data lock up to Day 42 data in Group 1 and Group 2. If the efficacy may be inadequate or unconfirmable in Group 1 after key open, public vaccination will be recommended. After key open, public vaccination will be recommended in Group 2. If subject receives the vaccination, the subject will be withdrawn from the study prior to public vaccination.

5.6 Interim report

After unblinding, an interim report may be prepared with results of Group 1 and Group 2 only.

6 PLANNED NUMBER OF SUBJECTS AND STUDY PERIOD

6.1 Planned Number of Subjects

145 subjects will be enrolled.

Group 1: Subjects will receive 3.75 μ g of MT-2766 in a final volume of 0.5 mL (n = 100).

Group 2: Subjects will receive placebo for MT-2766 3.75 μ g in a final volume of 0.5 mL (n = 25).

Group 3: Subjects will receive 1.875 μ g of MT-2766 in a final volume of 0.25 mL (n = 20).

The sample size is not based on power calculations but is set to meet the objectives of this clinical study.

For Group 3, the study may be completed even if fewer than 20 subjects are enrolled.

6.2 Study Period

The planned duration of the study is approximately 14 months, from screening procedures up to the end of the study.

7 INVESTIGATIONAL PRODUCT

7.1 Investigational Product

7.1.1 MT-2766

MT-2766 is the CoVLP vaccine composed of recombinant spike (S) glycoproteins expressed as VLPs with 1:1 (v:v) ratio of the adjuvant AS03 in a final volume of 0.25 mL (Group 3) or 0.5mL (Group 1).

For more information regarding the CoVLP formulation and AS03, refer to the current IB.

7.1.2 Placebo

The control product (placebo) will be composed of a phosphate-buffered saline solution (100 mM NaKPO₄, 150 mM NaCl) and 0.01 % polysorbate 80 at pH 7.4. The control product will be provided in vials.

Further specific information relating to the investigational product storage and shipment is provided in the Investigational Product Management Manual.

7.2 Study Vaccine Composition

The CoVLP vaccine is a sterile transparent to opalescent, colorless to yellowish liquid suspension. The CoVLP vaccine will be supplied in 3.1 mL multi dose vials. The S glycoprotein concentration in the vaccine will be 15 µg/mL for a final dosage of 3.75 µg in 0.25mL.

AS03 is an established effective adjuvant licensed for Arepanrix™ H1N1 and Arepanrix™ H5N1 (in Canada). The adjuvant is a whitish to yellowish homogeneous milky liquid emulsion and it will be provided in the original sterile vial container received from the manufacturer (GlaxoSmithKline). A 0.25 mL dose of AS03 represents one full human dose.

Further specific information relating to investigational product storage and shipment is provided in the Investigational Product Management Manual.

7.3 Investigational Product Packaging and Labeling

The CoVLP vaccine, AS03, and placebo will be packaged in separate boxes containing multiple vials of each investigational product.

The investigational product vials will have an English label as used in Medicago's Phase 2/3 study (CP-PRO-CoVLP-021). It is not possible to have a matching placebo in this study, therefore the vial labels will not be blinded. The study treatment will be prepared and administered by unblinded staff. Appropriate measures will be applied to maintain the observer-blindness of the blinded staff.

7.4 Preparation and Administration of Study Vaccine

The study treatments will be prepared by unblinded staff at the clinical site as described in the Preparation of Investigational Product Manual. The prepared study treatment will subsequently be administered to subjects by an unblinded staff. The unblinded staff must not be involved in the evaluation of any AEs or reactogenicity evaluations following vaccination.

The products to be used for study treatment administration will be handled in an aseptic manner.

The MT-2766 will be administered on study Day 0 and Day 21 as an IM injection of 0.5 mL (for subjects in Group 1 and Group 2) or 0.25 mL (for subjects in Group 3), into the deltoid muscle. For subjects, a 23 gauge needle of at least one inch or 2.5 cm in length can be used for vaccination.

The product administered will be recorded in study-specific documentation by the clinical site.

After drug accountability monitoring and reconciliation has been completed by the site and monitor, all study treatments (used and unused vials) will be returned to MTPC in accordance with instructions provided in the Investigational Product Management Manual.

Further specific information relating to investigational product storage, shipment and treatment preparation is provided in the Investigational Product Management Manual and Preparation of Investigational Product Manual.

7.5 Storage Conditions

The investigational products should be stored in an access-restricted area between 2 °C and 8 °C and protected from light; the vaccine should, however, be at room temperature before administration (i.e. the vaccine should not be administered cold and should be taken out of the refrigerator and brought to room temperature prior to administration).

The Investigational Product Management Manual provides additional details on storage of the investigational product.

7.6 Preparation, Handling, Storage, and Precautions for Use

After a clinical contract is concluded with the study site, MTPC will supply the investigational products. The investigational product manager will store and manage the investigational products in accordance with the Investigational Product Management Manual defined by MTPC.

The investigational product may not be used for any purpose not allowed in the protocol (e.g., other clinical studies, animal studies, basic research).

Further specific information relating to treatment preparation of investigational product is provided in the Preparation of Investigational Product Manual. The Investigational Product Management Manual provides additional details on handling and storage of the investigational product.

7.7 Drug Accountability

The head of the study site is responsible for ensuring that all study treatments received at the site are inventoried and accounted for throughout the study. The dispensing of study treatment to each subject must be documented on study-specific documentation.

The investigational products must be handled in strict accordance with the Investigational Product Management Manual and the vial label. The investigational products will be stored in a limited access area or in a locked cabinet under appropriate environmental conditions. The unblinded site staff will complete accountability for all investigational products (MT-2766 including CoVLP and AS03, and placebo). Refer to the Investigational Product Management Manual for details on the return of the used.

The study drug will be supplied only to subjects participating in the study. Returned study drugs may not be relabeled or reassigned for use for other subjects. The head of the study site agrees neither to dispense the study drug from, nor store it at, any site other than the study centers agreed upon with MTPC.

7.8 Procedures for Emergency Code Break

Any code break will be documented and reported to the MTPC in a timely manner by the Investigator. In a medical emergency, the Investigator may unblind the treatment for that subject without prior consultation with MTPC. The Investigator will open the emergency code in accordance with the "Procedure for Emergency Code Break" to identify the treatment group. In this procedure, the Investigator will disclose only the emergency code of the subject in question. In such an event, the Investigator will need to contact the Monitor as soon as possible after the unblinding to discuss the case. The treatment allocation should not be disclosed by the Investigator to the Monitor. In addition, the Investigator will prepare a document describing the reasons for the break and the range of CRFs that have been fixed before the break and submit it to MTPC.

MTPC will open the emergency code in accordance with the "Procedure for Emergency Code Break" to identify the treatment group. MTPC will record the reason for the break and the contents of deliberation and store them appropriately. MTPC will report the break to the Investigator and Medicago.

If a subject requests to participate in public vaccination before key open, the (sub)investigator must notify the emergency contact center in writing of the request and the subject identification code to be unblinded. The emergency contact center will unblind only the subject and identify the treatment group according to "Procedure for Emergency Code Break". The emergency contact center will notify the treatment group of the subject to the (sub)investigator. The (sub)investigator will inform the subject of the treatment allocation results. The emergency contact center will inform MTPC that the emergency key has been broken. Upon unblinding of a subject's treatment allocation, the subject will be withdrawn from the study and a withdrawal visit will be performed according to the withdrawal procedure (see Section 13.6).

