13.6 Withdrawal Procedure

Withdrawal subjects will be those who leave the study before Day 386, for whatever reason; withdrawal subjects will not be replaced. Any subject who withdraws the study will be asked to undergo Day 128 visit procedures within two weeks of withdrawal, if the subject agrees. If a subject is withdrawn from Day 1 to Day 29, solicited local/systemic AEs are investigated. If a subject is withdrawn from Day 1 to Day 49, unsolicited AEs are investigated. If deemed necessary by (sub)investigator, necessary tests such as biochemistry, hematology, or urinalysis will be performed.

All withdrawal subjects must be reported to MTPC. The reason for withdrawal should be documented in the subjects' records and in the appropriate section of the eCRF. The eCRF must be completed up to and including the time of the drop-out/final assessment.

The (sub)Investigator or clinical research coordinator will record the date of discontinuation, reason for discontinuation, etc. in the case report form. Furthermore, if the study is discontinued because of an adverse event, the (sub)Investigator or study coordinator will record the term of the event that resulted in discontinuation in the case report form. The date of discontinuation will be the date on which the (sub)Investigator made the decision to discontinue the study and informed the subject that the subject was being discontinued from the study; however, if the (sub)investigator is not able to get ahold of the subject, then the date of discontinuation will be the date on which the decision was made to discontinue the subject from the study.

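### A public-vaccination request before key open unblinds the (sub)investigator and the subject before the withdrawal visit, so adverse events still open at that moment can be assessed unblinded

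*Protocol*

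**What the plan says.** Protocol 7.8 describes two routes to an individual code break: a medical emergency and an elective request. The elective route opens with "If a subject requests to participate in public vaccination before key open, the (sub)investigator must notify the emergency contact center in writing". The center breaks the code for that subject only, and the steps then run in this order:

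1. "The emergency contact center will notify the treatment group of the subject to the (sub)investigator".
2. "The (sub)investigator will inform the subject of the treatment allocation results".
3. On unblinding, "the subject will be withdrawn from the study and a withdrawal visit will be performed according to the withdrawal procedure".

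Protocol 13.6 defines that procedure. The subject "will be asked to undergo Day 128 visit procedures within two weeks of withdrawal, if the subject agrees". Solicited events are looked into if withdrawal falls between Day 1 and Day 29. For unsolicited events the text reads "If a subject is withdrawn from Day 1 to Day 49, unsolicited AEs are investigated".

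Four other places bear on the point:

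- Protocol 5.4.2 gives the general rule: "Until key code breaking of the study, the following individuals will not have access to treatment allocation". Those listed include the subjects and the investigators. The elective route is not mentioned.
- In the emergency paragraph of 7.8 the investigator must document the reason for the break and "the range of CRFs that have been fixed before the break". The elective paragraph does not repeat this.
- Protocol 13.4 asks for the withdrawal procedures to come before the public vaccination where possible. It does not place them before disclosure.
- SAP section 5 keeps every dosed subject in the safety set. The SAP has no rule for adverse event records made after an individual code break.

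**The concern.** Severity of solicited events, and severity and causality of unsolicited events, are primary safety endpoints (Protocol 2.2.1). Protocol 5.3.2 gives reduction of bias in data collection and endpoint evaluation as the reason for the observer blind. The plan guards that blind elsewhere: staff who prepare and give the injections are kept out of adverse event evaluation (5.4.2, 7.4), and telephone safety contacts are made by blinded staff (9.3.4, 9.3.11).

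The elective route works the other way. Nothing about it is described as urgent, yet the subject who grades solicited events and the (sub)investigator are told the arm first, and a visit that collects adverse events follows. No text requires outstanding entries to be completed before the code is released, or names a separate blinded assessor for that visit. At stake is the blinded status of the last adverse event assessment for each such subject, in a comparison with only 25 placebo subjects.

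**Working it through.** The point concerns the order of steps, so the check is mainly a side-by-side reading. The plan states no figure here other than the group sizes, and these reproduce: 125 × 4/5 = 100 and 125 × 1/5 = 25.

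**Does the withdrawal visit reach the primary windows?** From Protocol 2.2.1, the solicited windows end nominally at Day 0 + 7 = 7 and Day 21 + 7 = 28. The unsolicited windows end at Day 0 + 21 = 21 and Day 21 + 21 = 42. The ranges in 13.6 run to Day 29 and Day 49, that is 29 − 28 = 1 day and 49 − 42 = 7 days past the last window. So both sets of windows are covered.

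**Who assesses at that visit?** Subjects grade solicited events (Protocol 11.1.1). The investigator attributes unsolicited events, while solicited events count as related by rule (12.1.9). The Day 128 procedures used for withdrawal (9.3.12) include review of the memory aid, with corrections made by the subject, a review of safety data, and a physical examination by the investigator or sub-investigator.

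**What has already been captured blind?** Diaries are completed daily through Day 7 after each dose (9.3.3.3, 11.1.1). Blinded staff make contact on Days 1, 8, 15, 22, 29 and 36 (9.3.4, 9.3.7). Site visits fall on Days 3, 21, 24 and 42. The longest nominal gap is 15 − 8 = 7 days, and likewise 36 − 29 = 7 days. At the code break, the unrecorded part is therefore mainly what has arisen since the last contact. The visit itself may follow up to two weeks after withdrawal.

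**What is open to unblinded assessment?**

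| State at the code break | Solicited | Unsolicited |
|---|---|---|
| Recorded, graded, not changed later | Blind | Blind |
| Recorded, but completed or changed later | Grade | Grade and causality |
| Not yet recorded | Occurrence and grade | Occurrence, grade and causality |

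The middle row matters for solicited events because SAP 7.1.3.1.1 (Solicited Adverse Events) gives the investigator's assessment precedence over the diary whenever one exists. It sets no limit relative to a code break, so an assessment entered after disclosure could replace a blind diary grade.

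**When does the request matter?** Up to about Day 42, window events may still be outstanding. Key open waits for all of Groups 1 and 2 to reach Day 42 and for a data lock (Protocol 5.2, 5.5), so a subject can also ask later than that. Then only window events reported late or re-assessed are exposed.

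**Scale.** One placebo subject is 1/25 = 4.0 percentage points of incidence, and one MT-2766 subject is 1/100 = 1.0 point. If, as an assumption, 1 to 5 placebo subjects had an event status that rested wholly on the post-disclosure assessment, the placebo incidence could move by at most 1/25 = 4 to 5/25 = 20 points. For comparison, the exact (Clopper-Pearson) 95% interval is 0 to 13.7% for 0/25, 0.1 to 20.4% for 1/25 and 6.8 to 40.7% for 5/25. A change in one subject therefore lies within the sampling uncertainty of the placebo arm.

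**The case against.** The strongest case on the other side is that little is left to bias. Diaries are filled in the same day, and blinded contacts are at most 7 days apart nominally. Case report forms are submitted promptly, and changes need a stated reason and leave an audit trail (Protocol 18.3, 18.4). Grading uses millimetre, temperature and functional criteria (11.1.1), and solicited events carry no causality judgement. The safety summaries are descriptive, with no test or decision threshold. All of this stands, and it limits the point to entries that are outstanding or changed later.

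Three stronger readings are tempting, and the documents do not support them:

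- *That all primary-window events of such a subject are assessed unblinded.* Those captured before the break were not.
- *That 7.8 contradicts 5.4.2.* Section 5.4.2 is the general rule and 7.8 a specific exception, as it is for emergencies. What is missing is a cross-reference.
- *That the emergency route has a safeguard against unblinded assessment which the elective route lacks.* The emergency record states what was already final; it does not require anything to be finalised first. Every code break must in any case be documented and reported under the opening sentence of 7.8, and the separate code-break procedure, which is not among the documents, may say more.

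It is also fair that 7.8 does not say the (sub)investigator who is told the arm must be the one who assesses events at the visit. The text permits unblinded assessment; it does not prescribe it. Finally, the visit is voluntary, so a rule that made disclosure wait for it would put pressure on a subject who is free to leave. The fix has to allow for that.

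**Conclusion.** The point holds in a limited form. On the elective route, disclosure to the (sub)investigator and the subject precedes a visit that collects adverse events in the primary windows. Nothing in the protocol or SAP requires outstanding entries to be finished blind, or identifies those that were not. The order of steps is plain from the text; how much bias follows is not known.

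The figures of 4 points per placebo subject and 1 point per MT-2766 subject measure exposure. A reader might infer an expected bias of 4 to 20 points in the placebo rate. That would need a request rate, which the documents do not give, and every requester's event status would have to depend on the last assessment, which the schedule of diaries and contacts makes unlikely. A reader might also infer that requests would cluster among placebo subjects who had no reaction. That is plausible, but nothing in the documents shows it.

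The finding does not undermine the safety analysis. The change is still worth making because the subject is withdrawn on unblinding in any case, so assessing first costs little.

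**What to change.** 1. In Protocol 7.8, for requests that are not medical emergencies, have outstanding adverse event collection, grading and (for unsolicited events) causality completed, and those eCRF pages fixed, while the site is still blind. Do this at the withdrawal visit, or by phone contact if the subject declines the visit. Only then does the (sub)investigator ask the contact center to release the code.
2. State that disclosure is not conditional on a visit that the subject refuses.
3. Extend the emergency route's record of case report forms already final at the break to this route, and cross-refer 5.4.2 to 7.8.
4. In the SAP, flag adverse event records entered or changed after an individual code break, including investigator assessments of solicited events. The eCRF audit trail and the documented code break should supply the dates for eCRF entries.

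The cost is a paragraph of protocol wording and a derived flag. No visit is added, because the withdrawal visit is already planned and only moves ahead of disclosure. The downside is a short delay before the subject learns the allocation. SAP section 10 records that the study was discontinued; if data collection has ended, the flag is the part that can still be applied.
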